11. STATISTICAL METHODS

This study aims to demonstrate the superiority of an information message with positive content on the pain felt when a PIC is applied. The power is set at 80% to demonstrate a difference, with an alpha threshold of 0.05.

11.1 Hypothesis

First null hypothesis: The recorded intervention message has an effect comparable to that of the recorded control message on the painful feeling induced by the insertion of a PIC.

First alternative hypothesis: The recorded intervention message reduces the intensity and unpleasantness of the pain induced by a PIC insertion of at least 13 mm from the recorded control message.

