11.2 Determination of Sample Size

Based on a review of studies on pain during a PIC insertion (Baxter et al., 2009; Dutt-Gupta et al., 2007; Fossum et al., 2016; Fry et al., 2001; Hartstein et al., 2008; Kim et al., 2012; Marco et al., 2007; Ott et al., 2007), 2012; Soysal et al., 2005; Speirs et al., 2001; Witting et al., 2016), the mean pain intensity is estimated at 34 mm by the Visual Analog Scale (with a possible intensity between 0 and 100 mm), with a standard deviation estimated at 24 mm. To detect the smallest decrease in clinically significant pain intensity of 13 mm (Todd et al., 1996) due to the intervention, a sample of 110 patients, or 55 patients per arm, is required, with a power set at 80% and alpha set at 5%. Taking into account missing values or refusal to participate after randomization estimated at 10% of patients, 60 patients will be randomized per arm. A total of at least 240 patients will therefore be recruited for the two phases, i.e. the four arms, of the study.

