11.4.2 Primary Analysis

The primary analysis will compare the pain intensity and unpleasantness after the PIC insertion as measured by VAS. The VAS will be compared by Student t-test if the distribution is Gaussian or by Wilcoxon rank sum test if not. The analysis will be conducted according to the « intention to treat » principle, which will include all randomized patients.

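### Section 11.1 makes a reduction of at least 13 mm the alternative hypothesis, but the planned test is against no difference and 13 mm is only the sizing difference, so rejecting the null would not support the alternative as worded

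*Combined protocol and SAP*

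**What the plan says.** Section 11.1 sets out one pair of hypotheses, for the recorded messages. The null is: "The recorded intervention message has an effect comparable to that of the recorded control message". The alternative is: "The recorded intervention message reduces the intensity and unpleasantness of the pain induced by a PIC insertion of at least 13 mm".

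The other sections describe a plain superiority comparison:

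- Section 11 states the aim: "This study aims to demonstrate the superiority of an information message with positive content on the pain felt when a PIC is applied". It adds: "The power is set at 80% to demonstrate a difference, with an alpha threshold of 0.05".
- Section 11.2 gives 13 mm a planning role: "To detect the smallest decrease in clinically significant pain intensity of 13 mm", assuming an SD of 24 mm, it requires 55 patients per arm, raised to 60 for losses.
- Section 11.4.2 names the test: "The VAS will be compared by Student t-test if the distribution is Gaussian or by Wilcoxon rank sum test if not". It gives no margin, no shifted null and no rule comparing an interval with 13 mm.
- Section 4.2 asks only whether the positive message lowers pain intensity, without an amount.

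No section says how 13 mm is to be used when the result is interpreted.

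**The concern.** The two hypotheses do not meet. If the null means zero difference, true reductions between 0 and 13 mm belong to neither. If it is stretched to cover them, the planned test no longer tests it. Either way, rejecting a null of no difference supports a difference and does not by itself support one of 13 mm or more.

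This matters because section 11.2 treats 13 mm as the threshold of clinical relevance, and section 3.7 expects a positive result to be able to change practice and training. A literal reader of 11.1 could turn any significant result into a claim of clinical relevance. Wording the null as comparability, with no margin, invites the opposite error of taking a non-significant result to show that the messages are equivalent.

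**Working it through.** **Inputs.** Difference 13 mm, SD 24 mm, power 80%, alpha 0.05 and 55 per arm (section 11.2); 1:1 allocation (section 7.3); t-test against no difference (section 11.4.2). Section 11.2 does not state whether alpha is one- or two-sided. Reduction means control mean minus intervention mean.

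**1. Reproduce the plan's sample size.**

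- Normal approximation: n = 2 × (1.960 + 0.842)² × 24² / 13² = 53.5, or 54 per arm.
- t-test, two-sided 0.05: n = 54.5, or 55 per arm, which matches the plan.
- t-test, one-sided 0.05: n = 42.8, or 43 per arm, which does not match.

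The 55 per arm therefore belongs to a two-sided test of zero difference. Its power at a true 13 mm is 80.4%.

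**2. Smallest significant observed reduction.**

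- SE = 24 × √(2/55) = 4.58 mm.
- Critical value t(0.975, 108 df) = 1.982.
- Threshold = 1.982 × 4.58 = 9.07 mm. With all 60 per arm analysed, SE = 4.38 mm and the threshold is 8.68 mm.

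**3. What different observed reductions would support (55 per arm).** The 95% CI is the observed value ± 9.07 mm.

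| Observed reduction | 95% CI (mm) | Supports a reduction? | Supports at least 13 mm? |
|---|---|---|---|
| 8 mm | −1.1 to 17.1 | No | No, but 13 mm is not excluded |
| 9.1 mm | about 0 to 18.2 | Borderline | No |
| 13 mm | 3.9 to 22.1 | Yes | No |
| 22.1 mm | 13.0 to 31.2 | Yes | Yes |

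Results between about 9.1 and 22.1 mm are significant, but their interval includes values below 13 mm. In that range, 11.1 as worded and the data part company.

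In the other direction, observed reductions from about 3.9 mm (13 − 9.07) to 9.07 mm are non-significant, yet their interval still includes 13 mm. They would not show comparability.

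**4. Significance when the true reduction is below 13 mm.** The documents give no such value, so these are assumed. The chance of a significant result favouring the intervention is 19% at a true 5 mm, 41% at 8 mm and 58% at 10 mm.

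**The case against.** The strongest reply is that the pair follows a familiar convention. The alternative is written as the effect the trial is sized to detect, with an indifference zone between it and the null. On that reading, the planned test has about 80% power at exactly 13 mm and more beyond it, so 80% is the minimum power across the alternative as worded. This stands. A reader might infer that the stated power does not apply to the alternative, or that it covers any difference from zero. Neither is right: section 11.2 ties the power to 13 mm, and step 4 shows it is much lower for smaller effects.

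A reader might also infer that the investigators will present significance as proof of 13 mm. No section says so, and sections 4.2 and 11 point to a plain claim of reduction. Nor does any section say that non-significance in this comparison will be reported as comparability.

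A third tempting inference is that a directional alternative with unstated sidedness allows a one-sided test. The plan's own 55 per arm contradicts this, since a one-sided test needs only 43.

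The convention does not settle how the result is to be interpreted. Section 11.1 is where the plan defines its claim, it includes the 13 mm, and nothing in sections 11.4 or 11.5 limits what rejection of the null would mean.

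**Conclusion.** The concern holds as a mismatch between the alternative in 11.1 and the test in 11.4.2. The sample size, the power and the choice of test are not put in doubt by it. Accepting the alternative as written would be unsound for significant observed reductions between about 9.1 and 22.1 mm.

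It would go too far to say that the trial cannot establish a reduction of 13 mm. An observed reduction of about 22.1 mm or more would put the lower confidence limit there.

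The figures assume the planned SD of 24 mm, 55 analysed per arm and the t-test. Section 11.2 gives an SD for intensity only, so applying them to unpleasantness is an assumption. If Wilcoxon is used, the millimetre thresholds are approximate.

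**What to change.** In section 11.1, state the null as no difference between arms in post-insertion VAS and the alternative as a difference, with two-sided alpha 0.05. This wording fits both the t-test and the Wilcoxon option. Name 13 mm as the planning difference and the benchmark for clinical relevance, not as part of the tested claim.

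In section 11.4.2, add that:

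- the between-arm difference will be reported with its 95% CI, as a mean difference or, if Wilcoxon is used, a location-shift estimate;
- a significant result in favour of the intervention supports a reduction, and a reduction of at least 13 mm will be claimed only if the lower limit reaches 13 mm;
- a non-significant result will not be read as showing that the messages are comparable.

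The cost is a few sentences. Sample size, data collection and test are unchanged. The one downside is a less favourable claim from a significant result whose interval includes values below 13 mm.

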Outcome(s):	
The primary outcomes, i.e. the intensity and unpleasantness (emotional component) of the pain experienced by patients during PIC insertion, will be measured using a Visual Analog Scale (VAS). Patients' anxiety state, as a secondary outcome, will also be measured by VAS. These three measurements will be performed after the PIC is inserted using three rulers presented to patients.
 
Caregivers' assessment of patients' intensity and unpleasantness of pain and anxiety will also be measured using the three VAS, this time in paper format, and reported to the CRF after the PIC is placed. Patients and caregivers will be asked to rate their VAS without each other's knowledge.
 
Before inserting the PIC, patients will assess the intensity and unpleasantness of any pre-existing pain and their basal anxiety level with these same three VAS. This will give a baseline value for these three measures. These values will be reported in the CRF before the PIC is placed, along with the reason for consultation (internal medicine, traumatology or surgery) and any painkillers already given/ongoing in the ED.
 
Caregivers' behaviour will be assessed during the procedure according to the criteria described by Kaptchuck. The algic behaviour of patients during PIC insertion will also be evaluated using the Algoplus scale.
 
The procedure's characteristics (location, caliber, number of attempts, difficulties and complications encountered), the demographic characteristics of the patients (sex, age, origin, level of education) and the demographic characteristics of the caregivers (sex, age) will be reported in the CRF after the PIC is placed. Patients will also be asked two questions (« Are you generally afraid of needles? », « Do you suffer from chronic pain, i.e. that has lasted for more than 3 months? ») to contextualize their VAS and chronic analgesic use will be reported.
 
Finally, in the second phase, a unique coded number related to the study (study number) will be assigned to each caregiver and entered in the CRF when the PIC is placed. If needed, it will allow the analysis of data by clustering patients by caregiver.

Study design:	Interventional, prospective, randomised, active control, double blind (patient, caregiver, Co-investigator) for the first phase, single blind (patient) for the second phase.

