Statistical Considerations:	
Analyses will be performed using Stata software version 14 (StataCorp, TX, USA). Descriptive data will be presented by mean and standard deviation, median and interquartile space or proportions for Gaussian, non-Gaussian, and categorical variables, respectively. The comparison between randomized groups will be done by Student t-test or Wilcoxon rank sum test for continuous variables, and by Chi2 or Fisher exact test for categorical variables, as appropriate.
 
This study aims to demonstrate the superiority of an information message with a positive content on the pain intensity when a PIC is inserted. The mean intensity of pain is estimated at 34 mm using a VAS (with a possible intensity between 0 and 100 mm), with a standard deviation estimated at 24 mm when a PIC is placed. To detect the smallest decrease in clinically significant pain intensity of 13 mm caused by the procedure, a sample of 110 patients, or 55 patients per arm, is required, setting the power at 80%, with an alpha threshold of 0.05. Taking into account missing values or refusal to participate after randomization estimated at 10% of patients, 60 patients will be randomized per arm. A total of at least 240 patients will therefore be recruited for the two phases, i.e. the four arms, of the study.

GCP Statement:	The study will be carried out in accordance to the protocol and with principles enunciated in the current version of the Declaration of Helsinki, the guidelines of Good Clinical Practice (GCP) issued by ICH, the Swiss Law and Swiss regulatory authority's requirements.

ABBREVIATIONS

CA	Competent Authority (e.g. Swissmedic)
CEC	Competent Ethics Committee
ClinO	Ordinance on Clinical Trials in Human Research
CRF	Case Report Form
ER	Emergency room
FOPH	Federal Office of Public Health
GCP	Good Clinical Practice
HFG	Humanforschungsgesetz (Law on human research)
HMG	Heilmittelgesetz (Law on medicines)
ICH	International Conference on Harmonisation of Technical Requirements for Registration of Pharmaceuticals for Human Use
ICTRP	International Clinical Trials Registry Platform
ISO	International Organisation for Standardisation
IUMSP	Institut Universitaire de Médecine Sociale et Préventive (University Institute of Social and Preventive Medicine)
Kofam	Koordinationsstelle Forschung am Menschen (Coordination Office Research on Human Beings)
LPTH	Loi sur les produits thérapeutiques (Therapeutic Products Act)

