4.2 Primary Objective

The primary objective of this study is to determine if the use of a positive information, avoiding negative words and suggesting specific notions of control and comfort related to the procedure, when inserting a PIC in the ED, reduces pain intensity when compared to the usual language practices.

The primary objective is also to determine if this effect is comparable, whether the message is delivered by a standardized audio recording or by the caregiver performing the procedure.

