5. STUDY OUTCOMES

5.1 Primary Outcomes

The primary outcome of this study will be patients' assessment of the intensity and unpleasantness (emotional component) of their pain during the insertion of the PIC.

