9.2 Assessments of outcomes

9.2.1 Assessment of primary and secondary outcomes

The primary outcomes, the intensity and unpleasantness (emotional component) of pain experienced by patients during the PIC insertion, will be measured using a Visual Analog Scale (VAS) (Lang et al., 2014; Pagé et al., 2012). Patients' anxiety, as a secondary outcome, will also be measured by VAS. These three measurements will be performed by using three rulers after the PIC is inserted. These three rulers, with three different color codes to distinguish them, will be presented to the patients who will move the three sliders on a line going from one extreme to the other (No pain / Worst pain imaginable; Experience not at all unpleasant / Most unpleasant experience possible; Not at all anxious / Extremely anxious) and corresponding, on their other side, to a value between 0 and 100 mm on a 100 mm long line. This numerical value measured in millimetres will be reported in the CRF by the co-investigators. Patients will be asked to rate their overall feelings after the PIC insertion regarding these three aspects. The co-investigators will ensure that the caregivers do not become aware of the patients' responses.

As for caregivers' assessment of patients' pain intensity and unpleasantness and anxiety, these secondary outcomes will also be measured using the three VAS, this time in paper format and reported in the CRF after the PIC insertion. Caregivers will mark their estimation by tracing a line on each of the three VAS once they have completed their procedure, making sure that patients do not read their answers. The co-investigators will then measure the distance between the 0 extreme and the line traced by the caregivers in millimetres and report this numerical value in the CRF.

Before the PIC insertion, patients will assess the intensity and unpleasantness of any pre-existing pain and their basal anxiety level with these same three VAS. This will give a baseline value for these three measures. These values will be reported in the CRF before the PIC is inserted, along with the reason for consultation (internal medicine, traumatology or surgery) and any painkillers already given/ongoing in the ED.

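### Intensity and unpleasantness of pain are both primary, but the trial is sized on intensity alone and no success rule, order or alpha split is stated

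*Combined protocol and SAP*

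**What the plan says.** Some parts of the document rest on intensity alone:

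- Section 4.2 asks whether positive information "reduces pain intensity when compared to the usual language practices".
- The synopsis (Statistical Considerations) aims at "superiority of an information message with a positive content on the pain intensity when a PIC is inserted".
- Section 11.2 plans "To detect the smallest decrease in clinically significant pain intensity of 13 mm", with mean 34 mm, SD 24 mm, 80% power and alpha 5%. This gives 55 per arm, with 60 per arm randomised to allow for 10% loss.

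Other parts make both measures primary:

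- The synopsis (Outcomes) has "The primary outcomes, i.e. the intensity and unpleasantness (emotional component) of the pain experienced by patients during PIC insertion", and 9.2.1 has "The primary outcomes, the intensity and unpleasantness (emotional component) of pain experienced by patients during the PIC insertion". Both use the plural.
- Section 5.1 uses the singular for the pair: "intensity and unpleasantness (emotional component) of their pain during the insertion of the PIC".
- The alternative in 11.1, for the audio phase, is that the positive version "reduces the intensity and unpleasantness of the pain induced by a PIC insertion of at least 13 mm from the recorded control message". The null in 11.1 does not separate the two measures.
- Section 11.4.2 states: "The primary analysis will compare the pain intensity and unpleasantness after the PIC insertion as measured by VAS".
- Section 11.5 treats the pair as the primary endpoint when it sets the missing-data rule.

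The two are separate ratings on separate rulers (9.2.1), so the primary analysis makes two comparisons. Section 11 gives one power and one alpha. Sections 11.1 to 11.5 give no success rule, testing order or alpha split, and no SD or correlation for unpleasantness.

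**The concern.** With two primary comparisons and one alpha, the plan must say what counts as success. If one comparison is significant and the other is not, a reader cannot tell from the document whether the primary claim is met, and the rule could be settled after the results are known. Blinding the analyst to arm labels (11.4) does not prevent this, because the p-values show which outcome succeeded. Section 11.4.6 promises to report deviations, but adopting a rule where none was written need not count as one.

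The stated operating characteristics also depend on the missing rule. The 80% power was calculated for intensity. It does not carry over to a joint claim, and the 0.05 does not carry over to a claim on whichever outcome succeeds.

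**Working it through.** **Inputs from 11.2:** difference 13 mm, SD 24 mm, alpha 0.05, power 80%, 55 evaluable and 60 randomised per arm, 10% loss. **From 11.1:** at least 13 mm, read naturally as applying to both measures. **Assumed, because the document is silent:** two-sided tests; SD 24 mm for unpleasantness; correlation r between the two ratings from 0.3 to 0.9. All figures are for t-tests, per phase.

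**1. The plan's own figure.** SE = 24 × √(2/55) = 4.577 mm. Noncentrality = 13/4.577 = 2.84 with 108 df and critical t = 1.982. Power is 0.804 at 55 per arm and 0.796 at 54, so 55 is the smallest number reaching 80%. A one-sided 0.05 test would need only 43 (normal approximation), which is why two-sided testing is inferred. The sample size is therefore that of one two-sided test of one outcome. Allowing for loss, 60 × 0.90 = 54 per arm, with power 0.796.

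**2. Both required.** Joint power cannot exceed the smaller of the two separate powers. With a 13 mm intensity effect it is at most 0.804. The power for unpleasantness alone is 0.581 at 10 mm, 0.804 at 13 mm and 0.991 at 20 mm. Simulating correlated t-statistics (2,000,000 runs, 55 per arm, intensity effect 13 mm) gives:

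| Unpleasantness effect | Result | r = 0.3 | r = 0.5 | r = 0.7 | r = 0.9 |
|---|---|---|---|---|---|
| 13 mm | both significant | 0.671 | 0.692 | 0.717 | 0.754 |
| 13 mm | exactly one | 0.265 | 0.224 | 0.173 | 0.100 |
| 20 mm | both significant | 0.799 | 0.801 | 0.803 | 0.804 |
| 20 mm | exactly one | 0.197 | 0.193 | 0.189 | 0.187 |
| 10 mm (sensitivity only) | both significant | 0.500 | 0.524 | 0.549 | 0.576 |
| 10 mm (sensitivity only) | exactly one | 0.385 | 0.337 | 0.286 | 0.233 |

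The rows are linked by P(exactly one) = p1 + p2 − 2 × P(both). For 13 mm at r = 0.9, this is 0.804 + 0.804 − 2 × 0.754 = 0.100.

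**3. Either accepted at 0.05.** When neither outcome is affected, P(either) = 0.05 + 0.05 − P(both). Simulated P(both) is 0.005, 0.009, 0.016 and 0.030 for r = 0.3, 0.5, 0.7 and 0.9. P(either) is then 0.095, 0.091, 0.084 and 0.070.

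**4. Intensity first, then unpleasantness.** If neither outcome is affected, a false claim requires intensity to be significant first, so the chance of any false claim is 0.05 per phase.

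**5. Minor wording point in 11.1.** The planned test is against no difference. It becomes significant from an observed difference of about 1.982 × 4.577 = 9.07 mm, so a significant result does not establish a reduction of at least 13 mm.

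**The case against.** The strongest reply is that 11.1 already answers the question. Every place that names both measures joins them with 'and', and 5.1 and 11.5 treat the pair as one outcome or endpoint. On that reading both must improve, alpha stays at or below 0.05 without a split, and only joint power remains open. This has force, and it is the more natural reading. But 11.1 is a hypothesis rather than a decision rule, its null is not stated for each measure, and on that reading the 80% is not delivered at the hypothesised 13 mm on both.

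A second reply is that the intensity-only objective puts intensity first. Sections 5.1, 9.2.1 and 11.4.2 give the two equal status, so this too would need to be written down.

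A reader might infer more than the document supports in four respects:

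- **That the plan runs a type I error of 7% to 9.5%.** No section says that either outcome suffices. The figure shows what the silence permits; it is not a planned error rate.
- **That split results could reach 38%, or joint power fall to 50%.** These need an unpleasantness effect of 10 mm, below the value hypothesised in 11.1. They are sensitivity figures only.
- **That no unpleasantness effect is given.** Section 11.1 hypothesises at least 13 mm. What is missing is its SD and its correlation with intensity.
- **That the sample size is wrong.** For intensity alone, 55 per arm is correct.

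**Conclusion.** The concern stands as a missing rule and should be settled before data are seen. The primary objective and sample size concern one outcome; the outcome definitions, the alternative hypothesis and the primary analysis concern two.

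The 80% power at 0.05 is supported for intensity alone (0.804 at 55 per arm, 0.796 at 54). If both are required, power is about 67% to 75% with 13 mm on both, and about 80% if the unpleasantness effect is 20 mm. Across those two cases, a split result occurs in about 10% to 26% of trials per phase.

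The intensity-alone result follows from the plan's own inputs once two-sided testing is inferred. The joint figures also rest on an assumed SD of 24 mm for unpleasantness, a correlation of 0.3 to 0.9, and t-tests rather than the Wilcoxon alternative.

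**What to change.** **Preferred change.**

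- Name pain intensity as the single primary outcome in the synopsis, 5.1, 9.2.1, 11.1, 11.4.2 and 11.5, consistent with 4.2 and 11.2.
- Within each phase, test unpleasantness at 0.05 only if intensity is significant.
- Reword 11.1 as no difference versus a difference in pain intensity between the messages. State which phase it covers, since it now mentions only the recorded messages.
- Keep 13 mm as the planning difference only, and report the mean difference with its 95% confidence interval against 13 mm.

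**Alternative.** If the sponsor keeps both as co-primary, write into 11.1 and 11.4.2 that both must be significant at 0.05. Restate the 80% power as applying to intensity alone, and give the joint power with its assumptions.

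**Cost.** Neither option needs extra patients. Under the preferred change, unpleasantness loses equal status and cannot be claimed if intensity is not significant. Under the alternative, the sponsor accepts a joint power that may be below 80%. An amendment may count as substantial and then needs ethics committee approval and notice to the registries (2.3, 2.10).
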